### 6.2 Screening

Infants in the GA and PNA range will be screened for eligibility by the sites.

## 6.3 Enrollment

Research staff will obtain written informed consent from the parent/guardian.

### Screening/Pre-Dose Assessment

After the parent or legally authorized representative has signed the IRB-approved informed consent form and after it has been determined that the participant satisfies all inclusion and no exclusion criteria, the following evaluations will be recorded in the case report form (CRF):

1. Participant demographics
2. Medical history (from chart)
3. Concomitant medications
4. Physical examination, including weight
5. Laboratory determinations

## 6.4 Follow-up

### Assessments/Procedures (Day 1–4)

The following assessments will be conducted each day while the participant is on study:

1. Date and time of each study drug dose will be recorded
2. Concomitant medications
3. PK sampling
4. Laboratory and microbiologic determinations
5. Adverse events

Table 5 below provides the optimal plasma sampling collection windows for the study drug according to dosing interval. PK samples can be collected after dose 3, 4, 5, or 6. Every effort should be made to collect biological samples within these windows; however, samples obtained outside of the sampling windows are acceptable. Sample collection windows are relative to the end of the flush. PK samples should not be drawn during infusions or during the flush. The start and stop times of the flush will be recorded and will be ≤15 minutes. All study drugs will be administered over 30 minutes. Elimination samples will only be obtained around the last dose of study drug.

**Table 5.** Optimal Plasma Sampling Collection Windows for Study Drug by Dosing Interval

Sample #	Dosing interval (hours)			
	6	8	12	24
1	0–15 min*	0–15 min*	0–15 min*	0–15 min*
2	30–60 min	30–60 min	30–60 min	30–60 min
3	1–2 hr	1–2 hr	1–2 hr	1–3 hr
4	2–3 hr	2–3 hr	2–4 hr	3–6 hr
5	3–4 hr	3–4 hr	5–8 hr	6–12 hr
6	4–5 hr	4–6 hr	8–10 hr	12–18 hr
7	15 min prior to next dose			
8 (elimination)	12–18 hr	16–24 hr	24–36 hr	48–72 hr

\*End of flush.

**Priority PK samples:** At least 3 timed PK plasma samples at different time points should be collected per subject. Ideally 5 timed PK plasma samples should be collected per subject. Priority samples include # 2, 5, and 7 for each drug (see Table 5). For example, if an infant is receiving a drug every 8 hours, after the third dose the study coordinator collects sample #1, 2, and 6 and after the fourth dose the study coordinator collects sample #3, 4, 5, and 7.

**Flush times:** Flush times will be recorded and will occur  $\leq 15$  minutes from the end of study drug infusion.

**Minimizing blood loss:** Plasma samples will be collected in 200  $\mu\text{L}$  blood aliquots. To minimize the amount of blood sampling, a limited PK sampling scheme will be employed such that no more than 8 timed PK samples (1.6 mL of blood) are obtained from each participant for PK analysis.

**Dried Blood Spots (DBS) PK Sampling:** Collect 2 DBS samples at the same time as 2 of the timed plasma PK samples. If not enough blood is available for both samples, collect only timed plasma PK samples. DBS should be collected from the collected whole blood before spinning the samples for the plasma PK samples.

**Scavenge PK Sampling:** A maximum of 10 scavenged plasma samples will be collected per participant.

**CSF PK Measurements:** Collect 100-200  $\mu\text{L}$  of additional CSF into a cryovial tube from infants when CSF is obtained as part of clinical care from the time of first dose of study drug until 12 hours after the last dose. Alternatively, scavenged CSF samples (samples left over in the clinical microbiology lab) may be used.

**Urine Samples:** During one dosing interval when the timed multiple dose blood samples are obtained (after 3rd, 4th, or 5th), collect urine from the beginning of infusion to the next scheduled infusion.

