2. GA/PNA
  - i. Rifampin: <121 days PNA
  - ii. Ticarcillin-clavulanate: <91 days PNA AND <30 weeks GA
  - iii. Clindamycin: <121 days PNA AND <30 weeks GA
3. Sufficient intravascular access
4. Suspected systemic infection

OR

Receiving 1 of the study drugs per local standard of care

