## 7 STUDY PRODUCT DESCRIPTION

### 7.1 Dosage and Study Drug Information

#### 7.1.1 Rationale for Dose Selection

**Rifampin:** Infants receiving rifampin 5–10 mg/kg/day demonstrate wide inter-patient variability in rifampin concentrations, with some patients demonstrating low peak and trough plasma concentrations. A higher dose might provide higher therapeutic exposure without adverse effects. In addition, high inter-patient variability may lead to the need for rifampin therapeutic drug monitoring.

Record all doses of Rifampin, Ticarcillin-clavulante, or Clindamycin for up to 6 SOC doses prior to and including the first on-study dose after the informed consent is signed and any subsequent SOC doses through last dose. The last dose of study drug dosing is defined as the fourth dose for rifampin, and the sixth dose of clindamycin or ticarcillin-clavulanate after enrollment, even if the clinicians continue the study drug.

**Table 5.** Rifampin Dosing

Cohort	GA	PNA	Dose
1	<32 weeks	<14 days	10 mg/kg Q 24 hours x 4 doses
2	<32 weeks	≥14 days–120 days	15 mg/kg Q 24 hours x 4 doses
3	≥32 weeks	<14 days	15 mg/kg Q 24 hours x 4 doses
4	≥32 weeks	≥14 days–120 days	20 mg/kg Q 24 hours x 4 doses

**Ticarcillin-clavulanate** (based on ticarcillin component): Older infants receiving ticarcillin-clavulanate 50–100 mg (based on ticarcillin component) every 8 hours demonstrated wide variability in ticarcillin concentrations, with some patients demonstrating low peak and trough plasma concentrations. Premature infants will likely need a longer interval because of a lower CL.

**Table 6.** Ticarcillin Dosing

Cohort	GA	PNA	Dose
1	<30 weeks	<14 days	75 mg/kg Q12 hours x 6 doses
2	<30 weeks	≥14 days–45 days	75 mg/kg Q 8 hours x 6 doses
3	<30 weeks	>45 days–90 days	75 mg/kg Q 6 hours x 6 doses

All dosing regimens are similar to alternative published regimens.

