## 8 ASSESSMENT OF SAFETY

### 8.1 Methods and Timing for Assessing, Recording, and Analyzing Safety Parameters

Safety will be assessed from the time of informed consent through 72 hours after last study dose (adverse events) and 7 days after last study dose (serious adverse events, serious suspected adverse reactions, serious adverse reactions, suspected adverse reaction, adverse reactions). The last dose of study drug dosing is defined as the 4th dose of rifampin and the 6th dose of clindamycin or ticarcillin-clavulanate after enrollment, even if the clinicians continue the study drug. Safety will be assessed by frequency and incidence of adverse events (AEs) and serious AEs (SAEs). The BPCA data monitoring committee (DMC) convened by NICHD will review data and safety information from study participants on a quarterly basis.

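### Elimination sample 8 is timed from a last dose fixed by count, so an infant kept on the drug has two newer doses before it; rifampin's sample 8 also falls outside the protocol's PK sampling days

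*Protocol*

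**What the plan says.** - **When sample 8 is taken.** Section 6.4: "Elimination samples will only be obtained around the last dose of study drug". Table 5 in that section sets it at 12–18, 16–24, 24–36 or 48–72 h for 6-, 8-, 12- and 24-hour dosing, counted from the end of the flush. The same section adds: "PK samples should not be drawn during infusions or during the flush".
- **What the last dose is.** Section 7.1.1 sets it at the fourth dose for rifampin. For the other two drugs it adds: "and the sixth dose of clindamycin or ticarcillin-clavulanate after enrollment, even if the clinicians continue the study drug". Section 8.1 repeats the rule for all three drugs, again "even if the clinicians continue the study drug".
- **Which doses are recorded.** Section 7.1.1 covers standard-of-care doses before enrollment and "any subsequent SOC doses through last dose". Section 6.4, in a list headed Day 1–4, has: "Date and time of each study drug dose will be recorded". Section 7.1.5 asks for dose and frequency when the drug is given as clinical care. Section 7.2 has all drugs recorded on the CRF.
- **Which days have PK sampling.** The Section 6.4 list is headed Day 1–4. Table 4 ticks PK sampling only in the therapy column, Day 1–2/4.
- **Who may enter.** Inclusion criterion 4 in Section 5.2 admits infants with suspected systemic infection or "Receiving 1 of the study drugs per local standard of care".
- **What makes a sample evaluable.** Section 10.2 requires its dosing times and sample times.
- **What the samples feed.** Half-life is a primary outcome (Section 3.1.1). Section 10.3 plans non-compartmental analysis first, with a population model as the fallback.

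**The concern.** A sample labelled as elimination should follow a dose with no later dose in between. The protocol anchors it to a counted dose, foresees that dosing may go on past that count, and enrolls infants already on the drug as routine care. Nothing in the protocol makes drawing or using sample 8 depend on dosing having stopped.

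Two things are at stake. If the label is taken at face value, a concentration from a newer dose could enter the terminal slope of a primary outcome. If the sample goes to a population model instead, the model needs the times of the intervening doses, and the recording rule in Section 7.1.1 ends at the counted dose. For rifampin there is also a plain scheduling gap, which does not depend on continuation: the protocol's own sampling days end before sample 8 is due.

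**Working it through.** **Inputs.** Infusion 30 min, flush up to 15 min, and sample windows from Section 6.4; dosing intervals and counts from Section 7.1.1. The first on-study dose is set at hour 0 of Day 1, the flush at its 15-min maximum, so end of flush is 0.75 h after dose start. Day = integer part of (hours/24), plus 1.

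**Step 1: the protocol's own days.** The counted last dose starts at (n − 1) × interval. Rifampin: 3 × 24 = 72 h, Day 4; adding 7 days gives Day 11, as in Section 6.5. The six-dose regimens: 5 × 6 = 30 h and 5 × 8 = 40 h (Day 2), 5 × 12 = 60 h (Day 3). These fit the Day 1–2/4 column.

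**Step 2: windows as multiples of the interval.** 12–18/6, 16–24/8, 24–36/12 and 48–72/24 are each exactly 2 to 3.

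**Step 3: timeline if dosing continues on schedule.**

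| Interval | Counted last dose (h) | Further doses (h) | Sample 8 window (h) | Third further dose (h) |
|---|---|---|---|---|
| 6 h | 30 | 36, 42 | 42.75–48.75 | 48 |
| 8 h | 40 | 48, 56 | 56.75–64.75 | 64 |
| 12 h | 60 | 72, 84 | 84.75–96.75 | 96 |
| 24 h (rifampin) | 72 | 96, 120 | 120.75–144.75 | 144 |

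The window opens as the flush of the second further dose ends. Before the third infusion, sample 8 is 0 to 5.25, 7.25, 11.25 or 23.25 h after that newer dose, a range samples 1–7 already cover. The last 0.75 h of each window falls in the third infusion and flush, when sampling is not allowed.

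**Step 4: days.** Rifampin: further doses on Days 5 and 6, sample 8 on Days 6–7. The sample's days are the same whether or not dosing continues. For the other intervals, the further doses and sample 8 stay within Days 1–4, apart from the last 0.75 h of the 12-hour window.

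**Step 5: illustration of misuse.** This assumes one compartment and a log-linear fit forced through samples 6, 7 and 8. With k = ln 2 / half-life and x = time since a dose started, each dose contributes [(1 − exp(−k·min(x, 0.5)))/(0.5k)] × exp(−k·max(0, x − 0.5)), summed over doses. Half-lives are those quoted in Section 2.1. Sample 6 is at mid-window, sample 7 is 15 min before the next dose, and sample 8 is scanned over its whole window.

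| Case | Half-life (h) | Rising slope, no half-life | Falling, falsely long | Sampling not allowed |
|---|---|---|---|---|
| Clindamycin 8 h | 8.7 | 75.2% | 15.5% | 9.4% |
| Clindamycin 12 h | 8.7 | 82.6% | 11.2% | 6.3% |
| Clindamycin 6 h | 3.6 | 79.0% | 8.5% | 12.5% |
| Ticarcillin 12 h | 3.7 | 82.3% | 11.5% | 6.3% |
| Rifampin 24 h | 4.9 | 74.9% | 22.0% | 3.1% |

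No point in any window gives the right half-life. The least bad rifampin point is just before 144 h. Samples 6, 7 and 8 are then at 87.75, 95.75 and 144 h, with log concentrations relative to sample 7 of +8k, 0 and −0.25k. The mean time is 109.17 h, so the deviations are −21.42, −13.42 and 34.83. Slope = (−21.42 × 8k − 34.83 × 0.25k)/(458.7 + 180.0 + 1213.4) = −180.0k/1852 = −0.0972k. Half-life = 4.9/0.0972 = 50.4 h.

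**Step 6: what still works.** Samples 5–7 lie on one exponential within one interval and return the true half-life in all five cases. So do samples 6–8 when dosing has stopped.

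**The case against.** **The last dose may mean the true final one.** The word only in Section 6.4 and the elimination label suggest that, and the count definition sits in passages on dose recording and safety follow-up. But the definition is unqualified, appears twice, and holds despite continuation. Reading it the other way would move sample 8 still later, further beyond the sampling and recording days. Collection details may be in the manual of procedures, which is not shown.

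**The half-life harm needs a rule the protocol does not state.** This stands. A reader might infer from Step 5 that the trial's half-lives will be biased. The documents do not support that: Section 10.3 does not say which points enter the slope, and that choice normally belongs in an analysis plan. Sample 8 is not a priority sample (those are 2, 5 and 7). It would be at or above sample 7 over 83 to 96% of its window in the illustration, so the error would usually show.

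**Continued doses are captured elsewhere.** This stands in part. Section 7.1.5 records dose and frequency, and Table 4 ticks concomitant medications through Day 9/11. The Section 6.4 list applies on each day on study and can be read to cover further doses within Days 1–4. None of these clearly requires the clock time of each continued dose up to sample 8 for rifampin on Days 5–7. Under Section 10.2, a sample without dosing times is simply not evaluable, which points to loss of the sample more than to bias.

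**Large concentration ratios mislead.** This also stands. With continued dosing, sample 8 is about 90 times (ticarcillin) or 890 times (rifampin) the level in a stopped infant, but the denominator is nearly zero. For rifampin, 48–72 h is 48/4.9 = 9.8 to 72/4.9 = 14.7 half-lives. I give these ratios no weight.

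**Conclusion.** Two conflicts between stated rules hold, and both should be corrected.

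1. With the last dose fixed by count, sample 8 in an infant continued on schedule follows two newer doses and is not an elimination sample for the counted dose. The dose-recording rule in Section 7.1.1 stops at the counted dose, and the other recording passages do not clearly require the clock times that an evaluable sample needs.
2. Rifampin's sample 8, on Days 6–7, lies outside the Day 1–4 list and the only Table 4 column with PK sampling. It would be wrong to see this as a result of continuation; it applies to every rifampin infant.

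The likely effect is limited to a lost or misused non-priority sample. A biased half-life follows only if that sample is put in the terminal slope as labelled. The shares in Step 5 describe that case alone, and assume one compartment, on-schedule dosing and the half-lives quoted in Section 2.1. The share of infants continued is not stated, so no trial-wide effect can be computed. The timeline is certain given the schedule; its practical weight is only moderately so.

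**What to change.** - Reconcile Section 6.4, Section 7.1.1 and Table 4 so that PK sampling, and the date, time and amount of every dose of the study drug (including doses continued as clinical care), are covered up to the time of sample 8. For rifampin this means Days 5–7.
- State that sample 8 counts as an elimination sample in the non-compartmental analysis only if no further dose preceded it. Otherwise it is used only in a population model with the full dose history.

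The cost is a sentence in Section 6.4, aligned wording in Section 7.1.1 and the Table 4 PK row, and a few more dose times taken from the chart. Some infants will have no usable elimination sample. Treatment does not change.

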## 6.5 Final Study Visit

### Follow-up Assessment (Day 11)

For 7 days following the last dose of study drug, participants will be followed for the development of adverse reactions. These will be recorded on the CRF.

## 6.6 Laboratory Evaluations

### 6.6.1 Clinical Laboratory Evaluations

#### Laboratory Determinations

1. Any hematology values obtained within 72 hours prior to the first dose of study drug, while the participant is on study drug, and 72 hours after the last dose of study drug should be recorded. These include: hematocrit, white blood cell count, platelet count,

and differential. If multiple values for a laboratory are obtained in the 72 hours prior to first dose, record the value closest to enrollment.

2. Any serum chemistry values obtained within 72 hours prior to the first dose of study drug, while the participant is on therapy, and 72 hours after the last dose of study drug should be recorded. These include: BUN, calcium, potassium, sodium, aspartate aminotransferase (AST), alanine aminotransferase (ALT), alkaline phosphatase, total bilirubin, albumin, magnesium, chloride, and bicarbonate. If multiple values for a laboratory are obtained in the 72 hours prior to first dose, record the value closest to enrollment. The participant must have a baseline serum creatinine within 72 hours prior to first dose of study drug.

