#### **8.1.3 Identification of Events and Timeframe for Reporting**

As all participants in this study will have pre-existing medical conditions and will be currently hospitalized, those pre-existing conditions will not be considered as adverse events. New events that occur or worsening through frequency or intensity of pre-existing conditions will be reported as adverse events. All reportable events as defined above, determined to be an AE based on physical examination, laboratory findings, or other means, will be recorded in the source documents and entered in the electronic CRF (eCRF). Each event will be recorded on an AE case report form starting after consent has been obtained. The investigator will provide date of onset and resolution, severity, action(s) taken, changes in study drug dosing, causality to study drug, and outcome.

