### **Safety and Clinical Laboratory Analyses**

The number of AEs, suspected adverse reactions, and adverse reactions will be summarized overall, by severity, and by each Medical Dictionary for Regulatory Activities (MedDRA) system organ class and preferred term. Prior and concomitant medications will be summarized by World Health Organization (WHO) drug class. Laboratory data, such as hematology and serum chemistry data, will be tabulated by GA and PNA group. Summary statistics for changes from baseline will be presented. Continuous laboratory measurements will be described at each visit using univariable descriptive statistics (mean, median, etc.); observed values and changes from baseline will be summarized. Lab tests reflective of liver toxicity (e.g., ALT, AST) will be further summarized in terms of the most extreme values and largest changes from baseline (in the appropriate direction) observed from start of study drug through the end of therapy.

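### For infants already receiving the drug as standard of care, the Section 6.6.1 baseline rule can record an on-drug laboratory value and drop a pre-drug one, so changes from baseline may be understated

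*Protocol*

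**What the plan says.** All references are to the protocol.

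- **Entry (Section 5.2).** Suspected systemic infection qualifies an infant. So does the alternative: "Receiving 1 of the study drugs per local standard of care". No limit is set on earlier exposure.
- **Baseline laboratory values (Section 6.6.1).** The window is tied to study drug: "Any serum chemistry values obtained within 72 hours prior to the first dose of study drug". The text first asks for any value in that window, then narrows it: "If multiple values for a laboratory are obtained in the 72 hours prior to first dose, record the value closest to enrollment". The same rule is given for hematology and for chemistry.
- **Dose history and dose count (Section 7.1.1).** Standard-of-care doses are to be recorded "for up to 6 SOC doses prior to and including the first on-study dose after the informed consent is signed". The last study dose is the fourth for rifampin and, for the other two drugs, "the sixth dose of clindamycin or ticarcillin-clavulanate after enrollment, even if the clinicians continue the study drug". Section 8.1 repeats this count.
- **Terminology (Section 7.1.5).** Drug given in routine clinical care is also called study drug there.
- **Analysis (Section 10.3, safety and laboratory analyses).** By visit, "observed values and changes from baseline will be summarized". Liver tests are also summarized by their most extreme values and their largest changes from baseline. Tabulation is by gestational and postnatal age group.

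**The concern.** A laboratory baseline is meant to show the infant before the drug could have acted. If the window is anchored on the first dose after enrollment, part or all of it lies after the start of the drug for an infant who came in on standard-of-care treatment. Among several values the rule then favors the one nearest enrollment, which is usually the one with the most exposure behind it. Any drug-associated shift already present at that point is subtracted out of the change.

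Safety is the secondary outcome. The protocol's own risk sections list effects on liver tests, platelets and blood urea nitrogen, which are among the tests recorded under this rule. Because the rule governs what enters the case report form, a pre-drug value that is not recorded cannot be restored by a later analysis plan.

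**Working it through.** The plan states no figure on this point, so there is none to reproduce. The check is one of timing.

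**Inputs**
- Baseline window: 72 h before the first dose (Section 6.6.1).
- Dosing intervals: 24 h for rifampin; 12, 8 or 6 h by cohort for ticarcillin-clavulanate and clindamycin (Section 7.1.1 dosing tables). *Assumption:* earlier standard-of-care doses used the same intervals. Section 7.1.2 allows local dosing, so they may not have.
- Recorded earlier doses: 5 or 6, depending on whether the limit of 6 includes the first on-study dose (Section 7.1.1). This limits recording, not exposure.

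**Formulas.** With k earlier doses at interval τ, the first of them was given k × τ hours before the first on-study dose. The share of the window on drug is min(k × τ, 72) / 72. The number of earlier doses that fills the window is 72 / τ.

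| Interval | 5 earlier doses | 6 earlier doses | Doses that fill 72 h |
|---|---|---|---|
| 6 h | 30 h, 42% | 36 h, 50% | 12 |
| 8 h | 40 h, 56% | 48 h, 67% | 9 |
| 12 h | 60 h, 83% | 72 h, 100% | 6 |
| 24 h | 120 h, 100% | 144 h, 100% | 3 |

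For rifampin, three earlier doses are enough: 3 × 24 = 72 h. No pre-drug value can then fall in the window. At 6 or 8 h intervals with 5 earlier doses, 72 − 30 = 42 h and 72 − 40 = 32 h of the window are drug-free. A pre-drug value can exist there, but it loses to any later on-drug value nearer enrollment. The hours are not upper bounds, because a course longer than the recorded history is allowed.

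**Sensitivity (assumed values, not from the protocol).** Let s be the share of infants entering on drug and f the fraction of the eventual rise already present at their recorded baseline. If the true mean rise is the same in both groups, the mean change keeps 1 − s × f of its size:
- s = f = 0.25: 1 − 0.0625 = 0.94
- s = f = 0.50: 1 − 0.25 = 0.75
- s = f = 0.75: 1 − 0.5625 = 0.44

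If s is zero, nothing is lost. The protocol gives neither s nor f.

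**Which dose is the anchor.** Section 7.1.1 separates standard-of-care doses from the first on-study dose after consent, which supports the reading used above. Section 7.1.5 uses the term study drug for clinical-care doses too. If the first standard-of-care dose is the anchor, the window is pre-drug and the problem disappears. The value nearest enrollment would then simply be the last pre-drug one. Sites could read the rule either way.

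**The case against.** The strongest case against is this. The term is undefined, and one reading gives a pre-drug baseline. An enrollment baseline also measures change over the study dosing period, which is a defensible target when the study regimen may differ from the earlier care. These infants are sick and maturing, so a pre-course baseline would mix illness and recovery with drug effect, and the direction of bias is not certain. Splitting by exposure is ordinary analysis-plan material, and earlier doses are already recorded, so exposed infants can largely be identified.

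Much of this stands, and it is why the conclusion is worded as what may happen. Two parts do not answer the point. An undefined anchor is itself a reason to define it. And no analysis plan can use a pre-drug value that was never recorded; with the dose history capped, the start of a long course may not be known either.

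A reader might infer more than the documents support:
- *That toxicity is hidden.* Observed values at each visit and the most extreme liver values are reported whatever the baseline.
- *That every infant entering on standard of care is affected.* If the only value in the window came before the first dose of the course, the baseline is pre-drug.
- *That adverse event reporting is reset in the same way.* Section 8.1.3 does say that "those pre-existing conditions will not be considered as adverse events", but it goes on to make new events and worsening reportable, and Section 8.1.1 counts clinically significant laboratory changes. Starting collection at consent is ordinary practice.
- *That the rule also fails drug-naive infants.* Their candidate values are all pre-drug, and Table 4 allows Day 0 and Day 1 to be the same date. At most this is a minor matter of preference.

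**Conclusion.** The point holds in limited form. On the reading that Section 7.1.1 supports, the rule can give a previously exposed infant an on-drug baseline, always so for a rifampin infant with three or more earlier 24-hourly doses, and can discard a pre-drug value that was available. Changes and largest changes from baseline may then understate drug-associated change in these infants, who are summarized together with drug-naive infants as the protocol stands.

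The size is unknown. It depends on the share of infants entering on drug, on how much of any laboratory shift occurs before enrollment, and on the anchor that sites use. The hours above also assume standard-of-care intervals equal to those in the dosing tables. This is a descriptive secondary outcome of an uncontrolled study, so the point is a worthwhile, inexpensive improvement and not a threat to the primary pharmacokinetic aim.

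**What to change.** 1. In Section 6.6.1, state which dose anchors the 72-hour baseline window, and use the term study drug in the same sense in Sections 6.6.1, 7.1.1 and 7.1.5.
2. For infants with earlier standard-of-care exposure, record from the chart the date and time of the first dose of that drug in the current course and the last laboratory value before it, where one exists. Record this in addition to the last value before the first on-study dose.
3. In Section 10.3, present laboratory changes separately for drug-naive and previously exposed infants. Infants without a pre-course value need not be excluded; their change from the pre-study value can be shown and labeled as such.

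The cost is some rewording, chart look-back and two or three extra eCRF fields. No new blood draws are needed. The downsides are smaller subgroups, in age cohorts whose minimum is 4 evaluable infants (Section 5.1), and no pre-course value for some infants.

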### **Risks of Ticarcillin-clavulanate**

From the FDA label and review of the literature, side effects of ticarcillin-clavulanate, as with other penicillins, include the following adverse reactions: hypersensitivity (skin rash, pruritus, urticaria, arthralgia, myalgia, drug fever, chills, chest discomfort, erythema multiforme, toxic epidermal necrolysis, Stevens-Johnson syndrome, and anaphylactic reactions); central nervous system (headache, giddiness, neuromuscular hyperirritability, or convulsive seizures); gastrointestinal disturbances (disturbances of taste and smell, stomatitis, flatulence, nausea, vomiting and diarrhea, epigastric pain, and pseudomembranous colitis have been reported; onset of pseudomembranous colitis symptoms may occur during or after antibiotic treatment); hemic and lymphatic systems (thrombocytopenia, leukopenia, neutropenia, eosinophilia, reduction of hemoglobin or hematocrit, and prolongation of prothrombin time and bleeding time); abnormalities of hepatic function tests (elevation of serum aspartate aminotransferase [SGOT], serum alanine aminotransferase [SGPT], serum alkaline phosphatase, serum lactate dehydrogenase [LDH], serum bilirubin; there have been reports of transient hepatitis and cholestatic jaundice, as with some other penicillins and some cephalosporins); renal and urinary effects (hemorrhagic cystitis, elevation of serum creatinine and/or BUN, hypernatremia, reduction in serum potassium and uric acid); and local reactions (pain, burning, swelling, and induration at the infusion site and thrombophlebitis with intravenous administration).

Available safety data for pediatric patients treated with ticarcillin-clavulanate demonstrate a similar adverse event profile to that observed in adult patients.

Ticarcillin-clavulanate should not be used as monotherapy when methicillin-resistant *Staphylococcus aureus* is suspected.

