#### Exclusion Criteria

2. Allergic reactions:
  - i. Rifampin: history of allergic reactions to rifampin
  - ii. Ticarcillin-clavulanate: history of allergic reaction to any penicillin, cephalosporin, or clavulanate
  - iii. Clindamycin: history of allergic reaction to clindamycin
2. Urine output <0.5 mL/hr/kg over the prior 24 hours
3. Serum creatinine >1.7 mg/dl
4. Any condition that in the judgment of the investigator precludes participation because it could affect participant safety

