## 6 STUDY PROCEDURES

### 6.1 Summary of Procedures

**Table 4.** Schedule of Study Procedures and Assessments

	Screen 	Therapy 	Post Therapy (days)	
Time (Day)	-72 h – Day 0	Day 1–2/4	Day 3/5–9/11	EOT or Early Termination
Visit		1	2	3
Informed consent/assent	X			
Demographics	X			
Physical examination	X			
Medical history	X			
Serum creatinine	X			
Chemistry labs	X	X	X 	X
Hematology labs	X	X	X 	X
Microbiology labs	X	X	X 	
Study drug administration		X		
PK sampling 		X		
Adverse events		X	X	X
Concomitant medications		X	X	

Day 0 refers to time point prior to start of study drug but may be the same calendar date as day 1.

 Includes urine PK collection.

Labs need only to be collected up to 72 hours post last dose of study drug. EOT = end of treatment.

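### Serum creatinine is required at baseline but neither listed nor scheduled for recording afterwards, so change from baseline cannot be systematically tabulated

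*Protocol*

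**What the plan says.** Four parts of the protocol bear on this.

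- **Section 6.6.1, item 2** opens with a general rule covering "Any serum chemistry values obtained within 72 hours prior to the first dose of study drug, while the participant is on therapy" and the 72 hours after the last dose. It then gives the analytes: "These include: BUN, calcium, potassium, sodium, aspartate aminotransferase (AST), alanine aminotransferase (ALT), alkaline phosphatase, total bilirubin, albumin, magnesium, chloride, and bicarbonate". Creatinine comes in a separate sentence at the end of the item: "The participant must have a baseline serum creatinine within 72 hours prior to first dose of study drug".
- **Table 4 (section 6.1)** has a row labelled "Serum creatinine", distinct from the chemistry row, with one mark, at Screen. The chemistry row is marked at Screen, Therapy, Post Therapy and EOT. A footnote limits post-therapy laboratory collection to 72 hours after the last dose.
- **Section 5.2** makes creatinine an eligibility test. The exclusion is "Serum creatinine >1.7 mg/dl".
- **Sections 2.2.1 and 10.3** give the safety context. Among the ticarcillin-clavulanate risks is "elevation of serum creatinine and/or BUN". For laboratory data, the analysis section says: "Summary statistics for changes from baseline will be presented".

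**The concern.** The safety profile is the secondary outcome, and section 10.3 intends to describe laboratory safety partly through change from baseline. That needs at least one recorded value after dosing starts. Creatinine is the one chemistry test singled out as compulsory before the first dose, yet the recording list and the schedule both stop asking for it once treatment begins.

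For ticarcillin-clavulanate this meets a toxicity that the protocol itself names. If sites follow the list and the schedule literally, creatinine results produced on treatment by ordinary clinical care will stay in the chart and not reach the database. No statistical analysis plan can summarise values that were never recorded, so the matter has to be settled in the protocol and the eCRF.

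**Working it through.** No formula applies and the plan states no figure to reproduce. The check compares what is to be recorded with what is to be analysed.

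**1. The list.** The analytes named in 6.6.1 item 2 number 12: BUN, calcium, potassium, sodium, AST, ALT, alkaline phosphatase, total bilirubin, albumin, magnesium, chloride and bicarbonate. BUN is there; creatinine is not.

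**2. The schedule.**

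| Table 4 row | Screen | Therapy | Post Therapy | EOT | Marks after baseline |
|---|---|---|---|---|---|
| Chemistry labs | X | X | X | X | 3 of 3 |
| Serum creatinine | X | – | – | – | 0 of 3 |

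The schedule agrees with the list. Both treat creatinine as separate from the chemistry panel and attach it to baseline only.

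**3. The analysis.** A change from baseline is a later value minus the baseline value. Creatinine has one assured time point before the first dose and none after it, so the second term of the difference is not assured for any infant. BUN has both terms whenever it is obtained clinically.

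**4. The named risks (section 2.2.1).**

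| Drug | Renal effects listed | Creatinine named? |
|---|---|---|
| Ticarcillin-clavulanate | Includes raised creatinine and/or BUN | Yes |
| Rifampin | Raised BUN and serum uric acid | No |
| Clindamycin | Azotemia, oliguria and/or proteinuria, rare, with no direct relationship to renal damage established | No |

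The mismatch between a named toxicity and the recorded values is therefore explicit for ticarcillin-clavulanate only, the arm planned at 16 to 32 evaluable infants.

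**5. Other routes into the data.** Section 8.1.1 makes a change in routine laboratory results an adverse event if the investigator judges it clinically significant. Section 8.1.3 accepts laboratory findings as a source of adverse events, and section 8.1 collects these through 72 hours after the last dose. Section 10.3 then summarises them by severity and MedDRA term. A creatinine rise can reach the safety outcome this way, but as a judged event. It brings no distribution of values and no count of infants who had a post-baseline test.

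**The case against.** The strongest reply is that the governing sentence in 6.6.1 asks for any serum chemistry value obtained, and that the list is introduced by a verb that need not be exhaustive. Creatinine is a serum chemistry value and is discussed in the same item. On that reading it is recorded like the others whenever it is measured, and the separate sentence and Table 4 row only flag the one test that is compulsory because it decides eligibility. This reading is possible. Against it, the list is long and specific, includes BUN and omits creatinine, and the separate row is left blank after Screen. If both readings are open, sites may record differently, and that alone calls for clarification.

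Several stronger conclusions are tempting, and the protocol does not support them.

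- A reader might infer that the safety outcome cannot show a creatinine rise. It can, through adverse event reporting, and BUN remains as a partial renal marker.
- A reader might infer that there will be no on-treatment creatinine for any of the three drugs. The text shows only that none is assured.
- A reader might extend the named toxicity to rifampin and clindamycin. Their risk sections list renal effects without naming creatinine, and the rifampin section names BUN, which is recorded.
- A reader might argue that the baseline value will be too old to serve as a covariate for clearance. Section 6.4 allows PK sampling after dose 3, 4, 5 or 6, so no single age of that value follows. Which creatinine value enters a covariate analysis is a choice for the statistical analysis plan, which is not at hand. So is whether to tabulate the highest value.

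**Conclusion.** The point holds as a gap in data collection. Creatinine is compulsory before dosing, absent from the 12 named analytes, and marked in none of the three post-baseline columns of Table 4. Post-baseline creatinine is not assured, so the planned change from baseline cannot be systematically tabulated for a toxicity that the protocol names for ticarcillin-clavulanate. A rise would appear only if it is reported as an adverse event, or if a site reads the general recording rule broadly.

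This rests on two assumptions: that the eCRF follows the list and schedule as printed, and that some infants have creatinine measured in ordinary care during or soon after treatment. The protocol does not say how many, so the number of values at stake cannot be given. The primary PK outcomes are not called into question. The change is cheap and worthwhile, and it is best made before data collection, because unrecorded values are harder to recover later.

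**What to change.** Add serum creatinine to the analytes in 6.6.1 item 2, keeping the baseline requirement as it stands. In Table 4, mark the serum creatinine row under Therapy and Post Therapy, to 72 hours after the last dose, with a note that any value obtained for clinical care is to be recorded. Creatinine then enters the change-from-baseline summaries already planned in 10.3. Those summaries should show, by drug and GA/PNA group, how many infants had a post-baseline value.

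The cost is one eCRF laboratory field and some chart abstraction. No blood draw is added and no clinical rule changes. The limitation is that values will exist only where clinicians ordered the test, so the infants tested may not represent the whole group. That is why the number tested must be reported.
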